5.3 Meals and Dietary Restrictions

- 1. Participants should refrain from consumption of any nutrients known to modulate CYP enzyme activity (e.g., grapefruit or grapefruit juice, pomelo juice, star fruit, pomegranate, and Seville or Moro [blood] orange products) within 72 hours before the first administration of study drug, during the study, and until final discharge.
- 2. Diet should be generally stable during the study, e.g., new diet programs should not be initiated.

5.4 Caffeine, Alcohol, and Tobacco

- 1. During the outpatient portions of the study, participants should refrain from more than 2 standard units per day of alcohol for men or 1 unit/day for women, consumed no less than 3 hours prior to bedtime. Alcohol should not be consumed on PSG nights.
- 2. Moderate consumption of caffeinated beverages, containing up to a total of 400 mg caffeine per day, is permitted during the study period, consumed no less than 3 hours prior to bedtime.

5.5 Activity

There are no restrictions on physical activity during the study other than that physical activity should be generally stable during the study (e.g., new exercise programs should not be initiated).

5.6 Screen Failures

Screen failures are defined as participants who consent to participate in the clinical study but are not subsequently randomized to study treatment/entered into the study. A minimal set of screen failure information is required to ensure transparent reporting of screen failure participants that meets the Consolidated Standards of Reporting Trials publishing requirements and to respond to queries from regulatory authorities. Minimal information includes demography, screen failure details, eligibility criteria, and any serious adverse events (SAEs).

Individuals who do not meet the criteria for participation in this study (screen failure) will not be rescreened, except if the opportunity for rescreening has been enabled by protocol amendment.

6 Study Treatment

Study treatment is defined as any investigational treatment(s), marketed product(s), placebo, or medical device(s) intended to be administered to a study participant according to the study protocol.

6.1 Study Treatment(s) Administered

One tablet of co-formulated atomoxetine and R-oxybutynin or matching placebo is taken immediately before the participant's planned bedtime.

Study Treatment Name:	Atomoxetine hydrochloride/R- oxybutynin chloride	Atomoxetine hydrochloride/R- Oxybutynin chloride	Placebo
Dosage Formulation:	Tablet	Tablet	Tablet
Dosage Level:	37.5mg / 2.5mg	75mg / 2.5mg	N/A
Route of Administration:	Oral	Oral	Oral
Dosing Instructions:	1 tablet administered with up to 240 mL water	1 tablet administered with up to 240 mL water	1 tablet administered with up to 240 mL water
Storage/Packaging/Labeling:	Store at room temperature, in HDPE bottles	Store at room temperature in HDPE bottles	Store at room temperature in HDPE bottles

6.2 Preparation/Handling/Storage/Accountability

- 1. The Investigator or designee must maintain a log to confirm appropriate temperature conditions have been maintained during transit for all study treatments received and any discrepancies are reported and resolved before use of the study treatment.
- 2. Only participants enrolled in the study may receive study treatments and only authorized site staff may supply or administer study treatments. All study treatments must be stored in a secure, environmentally controlled, and monitored (manual or automated) area in accordance with the labeled storage conditions with access limited to the Investigator and authorized site staff.

- 3. The Investigator, institution, or the head of the medical institution (where applicable) is responsible for study treatment accountability, reconciliation, and record maintenance (i.e., receipt, reconciliation, and final disposition records).
- 4. After receiving Sponsor approval in writing, sites are responsible for returning all unused or partially used study treatment to the Sponsor or designated third party or for preparing the study treatment for destruction via incineration.

6.3 Measures to Minimize Bias: Randomization and Blinding

All participants will be centrally randomized for the crossover phase of the study. Each participant will be assigned a unique number (randomization number) that encodes the participant's assignment to 1 of the sequences of the study, according to the randomization schedule using a validated computer program.

Returned study treatment should not be redispensed to the participants.

In case of an emergency, the Investigator has the sole responsibility for determining if unblinding of a participant's study treatment assignment is warranted. Participant safety must always be the first consideration in making such a determination. If the Investigator decides that unblinding is warranted, the Investigator should make every effort to contact the Sponsor prior to unblinding a participant's study treatment assignment unless this could delay emergency treatment of the participant. If a participant's study treatment assignment is unblinded, the Sponsor must be notified within 24 hours after breaking the blind. The date and reason that the blind was broken must be recorded in the source documentation and electronic case report form (eCRF), as applicable.

In the event of a Quality Assurance audit, the auditor(s) will be allowed access to unblinded study treatment records at the site(s) to verify that randomization/dispensing has been done accurately.

6.4 Concomitant Therapy

Concomitant therapy with the medications listed below is disallowed. For medication that is typically used as-needed for symptomatic conditions (e.g. occasional use of a sleep aid), the medication should not be used for at least one week prior to the first study PSG and for the duration of the study.

• MAOIs or other drugs that affect monoamine concentrations (e.g., rasagiline) [MAOIs are contraindicated for use with atomoxetine]

- Selective Serotonin Reuptake Inhibitors (e.g., paroxetine)
- Selective Norepinephrine Reuptake Inhibitors (e.g., duloxetine)
- Norepinephrine Reuptake Inhibitors (e.g., reboxetine)
- Alpha-1 antagonists (e.g., tamsulosin)
- Tricyclic antidepressants (e.g., desipramine)
- CYP2D6 inhibitors
- Strong CYP3A4 inhibitors (e.g., ketoconazole)
- Benzodiazepines and other anxiolytics
- Opioids
- Sedatives including nonbenzodiazepine "Z-drugs" (zolpidem, zaleplon, eszopiclone)
- Muscle relaxants
- Pressor agents
- Drugs with clinically significant cardiac QT-interval prolonging effects
- Drugs known to lower seizure threshold (e.g., chloroquine)
- Amphetamines
- Antiepileptics
- Antiemetics
- Modafinil or armodafinil
- Beta₂ agonists, (e.g., albuterol)
- Antipsychotics
- Anticholinergics and anticholinesterase inhibitors, including drugs with substantial anticholinergic side effects, (e.g., first generation antihistamines)
- Sedating antihistamines
- Pseudoephedrine, phenylephrine, oxymetazoline
- Nicotine replacement products
- Most drugs for Parkinson's, Alzheimer's, Huntington's, Amyotrophic Lateral Sclerosis, or drugs for other neurodegenerative diseases

Medications that do not have substantial effects on the central nervous system (CNS), respiration, or muscle activity are generally allowed if dose and frequency is stable for 1 month prior to enrollment, including, but not necessarily limited to, the following drugs and drug classes:

- Antihypertensives (angiotensin-converting-enzyme/angiotensin II receptor blocker inhibitors, calcium channel blockers, spironolactone, hydrochlorothiazide, etc.)
- Statins
- Proton pump inhibitors and histamine h₂ receptor blockers
- Over-the-counter (OTC) antacids
- Non-sedating antihistamines (e.g., cetirizine, loratadine)
- Non-steroidal anti-inflammatory drugs and acetaminophen
- Laxatives
- Erectile dysfunction drugs
- Inhaled corticosteroids (e.g., fluticasone)
- Antidiabetics
- Ocular hypotensives and other ophthalmics (e.g., timolol)
- Hormonal therapy (e.g., estrogen replacement or anti-estrogens) and hormonal contraceptives
- Thyroid medications
- Anticoagulants
- OTC topicals (e.g., topical pain relievers)
- Osteoporosis drugs

6.5 Discontinuation of Study Treatment

If a clinically significant finding is identified, the Investigator or qualified designee will determine if the participant can continue in the study and if any change in participant management is needed. Any new clinically relevant finding should be reported as an adverse event (AE).

6.6 Stopping Criteria

6.6.1 Individual Participant Stopping Criteria

- Incidents of abuse, diversion, or misuse of the study treatment.
- Incidents of clinical significance: hallucinations, amnesia, delusional thinking, delirium, manic symptoms, aggressive behavior, suicidality, homicidality, agitation, confusion, or convulsions/seizures.
- Participants reporting any SAE considered possibly related or related to study treatment.
- Acute urinary obstruction.
- Any other AE that in the judgment of the Investigator necessitates the participant stopping to protect participant safety.

Participants discontinued from dosing will undergo end of study procedures with follow-up monitoring of the AE(s) as clinically indicated.

6.7 Participant Discontinuation/Withdrawal from the Study

- A participant may withdraw from the study at any time at his/her own request, or may be withdrawn at any time at the discretion of the Investigator for safety, behavioral, or administrative reasons.
- If the participant withdraws consent for disclosure of future information, the Sponsor may retain and continue to use any data collected before such a withdrawal of consent.
- If a participant withdraws from the study, he/she may request destruction of any samples taken and not tested, and the Investigator must document this in the site study records.
- All participants who withdraw from the study with an ongoing AE must be followed until the
 event is resolved or deemed stable.
- Participation may be terminated before completing the study and the reason recorded as follows:
 - Withdrawal due to AE
 - o Withdrawal due to incident abuse, diversion, or misuse of the study treatment
 - o Loss to follow-up
 - o Participant withdrew consent at own request

o Other

6.8 Loss of Participants to Follow-Up

A participant will be considered lost to follow-up if he or she repeatedly fails to return for scheduled visits and is unable to be contacted by the study site. The following actions must be taken if a participant fails to return to the clinic for a required study visit:

- The site must attempt to contact the participant and reschedule the missed visit as soon as possible (and within the visit window, where one is defined) and counsel the participant on the importance of maintaining the assigned visit schedule and ascertain whether or not the participant wishes to and/or should continue in the study.
- In cases in which the participant is deemed lost to follow-up, the Investigator or designee
 must make every effort to regain contact with the participant (where possible, 3 telephone
 calls and, if necessary, a certified letter to the participant's last known mailing address or
 local equivalent methods). These contact attempts should be documented in the participant's
 medical record/eCRF.
- Should the participant continue to be unreachable, he/she will be considered to have withdrawn from the study.

7 Study Assessments and Procedures

- Study procedures and their timing are summarized in the SoA.
- Adherence to the study design requirements, including those specified in the SoA, is essential and required for study conduct.
- All screening evaluations must be completed and reviewed to confirm that potential
 participants meet all eligibility criteria. The Investigator will maintain a screening log to
 record details of all participants screened and to confirm eligibility or record reasons for
 screening failure, as applicable.
- The maximum amount of blood collected from each participant over the duration of the study, excluding any extra assessments that may be required for safety or technical issues, will not exceed approximately 50 mL.
- Repeat or unscheduled samples may be taken for safety reasons or for technical issues with the samples, as per the Investigator or designee's discretion.

7.1.1 Polysomnography

- Methods: Standard overnight PSG recording and data interpretation will be performed in accordance with the American Academy of Sleep Medicine (AASM) scoring manual.
 Participants will be instrumented with standard PSG electrodes. Time of lights out will be established according to the participants' habitual schedule and kept constant across the PSG study nights. The participants will be given 8 hours of time-in bed.
- Scoring: All PSG studies (including screening PSG) will be scored by centralized PSG technologists, blinded to treatment assignment. Scoring will be conducted according to the American Academy of Sleep Medicine manual scoring criteria.

7.2 Safety Assessments

- Planned time points for all safety assessments are provided in the SoA.
- Safety monitoring will be guided by the established safety profiles of atomoxetine and
 oxybutynin, and by Phase 1 and 2 safety data for the combination. Safety assessments will
 include physical examinations, measurement of vital signs, monitoring and recording of AEs,
 SAEs, and pregnancies, recording of study or treatment discontinuations. Effects on OSA and
 sleep parameters (e.g., sleep time and sleep stages) will also be monitored by PSG.
- Adverse events of special interest include effects on urine outflow, as both atomoxetine and oxybutynin are associated with urinary retention. Effects of atomoxetine on heart rate and blood pressure are expected to be modest, as indicated by the initial data described above, and will also be monitored. Participants with serious cardiac abnormalities will be excluded from the study. Suicidal ideation in children and adolescents is a boxed warning for atomoxetine; however, analysis in adult patients, the target population for the proposed OSA study, did not reveal an increased risk of suicidal ideation or behavior in association with atomoxetine. Daytime sleepiness is both a potential safety outcome and efficacy outcome in OSA. Both atomoxetine and oxybutynin may be associated with somnolence, and oxybutynin is additionally associated with anticholinergic CNS effects such as memory difficulty.

7.2.1 Physical Examinations

• The general physical examination at screening includes an assessment of general appearance and a review of physical systems (dermatologic, head, eyes, ears, nose, mouth/throat/neck, thyroid, lymph nodes, respiratory, cardiovascular, gastrointestinal, extremities, musculoskeletal, neurologic, and psychiatric systems). Height and weight will also be measured and recorded (with shoes removed and wearing light indoor clothing).

• Investigators should pay special attention to clinical signs related to previous serious illnesses.

7.2.2 Vital Signs

- Assessment of vital signs (seated blood pressure, pulse rate, body temperature, respiratory rate) will be performed at the time points indicated in the SoA.
- Vital signs will be measured at all visits in a seated position after 5 minutes rest and will
 include temperature, respiratory rate, systolic and diastolic blood pressure, and pulse.
 Measurements should be made in the same arm of the participant at each visit.
- Systolic and diastolic blood pressure will be repeated for a total of 3 measurements, each at least 2 minutes apart.
- The method used to measure body temperature at screening should be maintained throughout the study for each participant, and should be indicated (e.g., ear, mouth, armpit).

7.2.3 Electrocardiograms

• A 12-lead ECG will be obtained using an ECG machine that automatically calculates the heart rate and measures the PR, QRS, and QT intervals. The ECG will be recorded in the semi-supine position after the participant has rested in this position for at least 10 minutes.

7.2.4 Clinical Safety Laboratory Assessments

- Refer to Section 9.2 for the list of clinical laboratory tests to be performed and to the SoA for the timing and frequency.
- The Investigator must review the laboratory report and document this review. The laboratory reports must be filed with the source documents.
- All protocol-required laboratory assessments must be conducted in accordance with the laboratory manual and the SoA.
- If laboratory values from laboratory assessments not specified in the protocol and performed at the institution's local laboratory result in the need for a change in participant management or are considered clinically relevant by the Investigator (e.g., are considered to be an SAE or an AE or require dose modification), then the results must be recorded in the eCRF.

7.3 Adverse Events and Serious Adverse Events

The definitions of AEs and SAEs can be found in Appendix 3.

Adverse events will be reported by the participant (or, when appropriate, by a caregiver, surrogate, or the participant's legally authorized representative).

The Investigator and any qualified designees are responsible for detecting, documenting, and reporting events that meet the definition of an AE or SAE and remain responsible for following up on AEs that are serious, considered related to the study treatment or the study, or that caused the participant to discontinue the study and/or study treatment.

7.3.1 Time Period and Frequency for Collecting AE and SAE Information

All AEs and SAEs will be collected from randomization until the end of the study at the timepoints specified in the SoA.

All SAEs will be recorded and reported to the Sponsor or designee within 24 hours, as indicated in Appendix 3. The Investigator will submit any updated SAE data to the Sponsor within 24 hours of it being available.

Investigators are not obligated to actively seek AEs or SAEs after the conclusion of study participation. However, if the Investigator learns of any SAE, including a death, at any time after a participant has been discharged from the study, and he/she considers the event to be reasonably related to the study treatment or study participation, the Investigator must promptly notify the Sponsor.

The method of recording, evaluating, and assessing causality of AEs and SAEs and the procedures for completing and transmitting SAE reports are provided in Appendix 3.

7.3.2 Method of Detecting AEs and SAEs

Care will be taken not to introduce bias when detecting AEs and/or SAEs. Open-ended and non-leading verbal questioning of the participant is the preferred method to inquire about AE occurrence.

7.3.3 Follow-up of AEs and SAEs

After the initial AE/SAE report, the Investigator is required to proactively follow each participant at subsequent visits/contacts. All SAEs will be followed until resolution, stabilization, until the

event is otherwise explained, or the participant is lost to follow-up. Further information on follow-up procedures is given in Appendix 3.

7.3.4 Regulatory Reporting Requirements for SAEs

- Prompt notification (within 24 hours, see Appendix 3) by the Investigator to the Sponsor of an SAE is essential so that legal obligations and ethical responsibilities towards the safety of participants and the safety of a study treatment under clinical investigation are met.
- The Sponsor has a legal responsibility to notify both the local regulatory authority and other
 regulatory agencies about the safety of a study treatment under clinical investigation. The
 Sponsor will comply with country-specific regulatory requirements relating to safety
 reporting to the regulatory authority, IRB/Independent Ethics Committees (IEC), and
 Investigators.
- Investigator safety reports must be prepared for suspected unexpected serious adverse reactions (SUSAR) according to local regulatory requirements and Sponsor policy and forwarded to Investigators as necessary.
- An Investigator who receives an Investigator safety report describing an SAE or other specific safety information (e.g., summary or listing of SAE) from the Sponsor will file it along with the Investigator's Brochure and will notify the IRB/IEC, if appropriate according to local requirements.

7.3.5 Pregnancy

- Details of all pregnancies in female participants after the start of study treatment and until at least 5 terminal half-lives after the last dose will be collected.
- If a pregnancy is reported, the Investigator should inform the Sponsor within 24 hours of learning of the pregnancy and should follow the procedures outlined in Appendix 4.
- Abnormal pregnancy outcomes (e.g., spontaneous abortion, fetal death, stillbirth, congenital anomalies, ectopic pregnancy) are considered to be SAEs.

7.4 Treatment of Overdose

For this study, any dose of atomoxetine hydrochloride greater than 75 mg and of R-oxybutynin chloride greater than 2.5 mg more frequently than QHS will be considered an overdose.

In the event of an overdose, the Investigator should refer to the approved product label for advice on overdose and:

- 1. Contact the Medical Monitor immediately.
- 2. Closely monitor the participant for AE/SAE and laboratory abnormalities until atomoxetine hydrochloride and/or R-oxybutynin chloride can no longer be detected systemically.
- 3. Obtain a plasma sample for PK analysis within 1 day from the date of the last dose of study treatment if requested by the Medical Monitor (determined on a case by case basis).
- 4. Document the quantity of the excess dose as well as the duration of the overdosing in the eCRF.

Decisions regarding dose interruptions or modifications will be made by the Investigator in consultation with the Medical Monitor based on the clinical evaluation of the participant.

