1.2 Schedule of Activities (SoA)

Table 1Schedule of Activities

	Screening		3-Way Crossover Period					End of Study Evaluation	
Procedures	V1	V2	V3	Wash-out	V4	Wash-out	V5	Wash-out	Evaluation
Trial Day (Visit Window)	Up to 4 weeks		Up to 6 weeks					2 wks post $V5 \pm 3 d$	
Informed consent	X								
Non-PSG enrollment criteria ²	X								
Demography	X								
Physical exam	X								
Medical history	X								
Clinical laboratory testing	X								X
Pregnancy test ³	X								
12 Lead ECG	X								
PSG Exam		X ⁴	X		X		X		
Randomization ⁵			X						
HS study treatment ⁶			X		X		X		
DSST, KSS, Sleep quality VAS ⁷			X		X		X		
Vital signs ⁸	X	X	X		X		X		
AE/SAE monitoring			X	X	X	X	X	X	X
Prior/concomitant medication	X	X	X	X	X	X	X	X	X

6 January 2021 7 of 54 V2.0

¹ Each washout period is a minimum of 7 days

² Includes ESS, PGI-S, and history of OSA symptoms

³ WOCBP only

⁴ Only patients who meet all non-PSG enrollment criteria at Visit 1 are eligible for a screening PSG

⁵ Randomization occurs when participant meets enrollment criteria up to the time of the first crossover period.

⁶ Study medication administered immediately before lights out

⁷ Administer at similar time after awakening after each crossover PSG, approximately 1 hour after awakening

⁸ Vital signs include the following: seated blood pressure, pulse, respiratory rate; vital signs on PSG nights taken after admission to PSG lab.

Clinical Study Protocol CONFIDENTIAL

Abbreviations: AE = adverse event; DSST = Digit Symbol Substitution Test; ECG = electrocardiogram; ESS = Epworth sleepiness scale; KSS = Karolinska sleepiness scale; PGI-S = patient global impression of severity of OSA; PSG = polysomnography; SAE = serious adverse event; VAS = visual analog scale; WOCBP = women of childbearing potential.

6 January 2021 8 of 54 V2.0

2 Introduction

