2.1 Study Rationale

Previous studies conducted by Apnimed (under IND 136752) and academic investigators support that the combination of atomoxetine and oxybutynin is safe and effective for the treatment of OSA. These initial Phase 2 studies of the combination were conducted with marketed oxybutynin (combination designated AD-036), which is a racemic mixture of R- and S-oxybutynin. Subsequent development (under IND 141505) is being pursued by Apnimed with R-oxybutynin (combination designated AD-109), a new enantiomerically pure form of oxybutynin which is proposed to have an improved safety and efficacy profile in OSA compared to racemic oxybutynin.

Previous studies of AD-036 provided dose-response efficacy and safety data across a range of doses. Doses of atomoxetine ranged between 25 mg and 80 mg, and doses of racemic oxybutynin between 1.5 and 5 mg. Combinations with the highest doses were clearly more effective than combinations with the lowest doses, with mid-range doses retaining substantial efficacy. All doses were safe and well-tolerated, with suggestion of positive correlation between dose and generally mild adverse effects. Study APC-004 is designed to extend and confirm these findings to AD-109, combining a dose of 2.5 mg R-oxybutynin with either 75 mg or 37.5 mg atomoxetine. Study APC-004 will enroll patients with mild- to moderate OSA, in parallel with other studies of AD-109 planned by Apnimed in moderate- to severe OSA.

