4.2 Scientific Rationale for Study Design and Dose

Previous Phase 2 studies conducted by Apnimed and academic collaborators support that the combination of atomoxetine and racemic oxybutynin is effective for OSA over a wide range of disease severity. This study will extend findings in patients with mild- to moderate OSA, whereas other planned studies will examine patients with moderate- to severe OSA.

This study is designed to provide additional dose ranging efficacy and safety data for doses of atomoxetine in the middle- and higher-range of doses previously studied. Completed studies of AD036 support efficacy and safety of 5 mg racemic oxybutynin in combination with atomoxetine. Because the R-enantiomer of oxybutynin confers about 2-fold the anticholinergic activity of the racemate, with such activity thought to be the major contributor to efficacy in OSA, the dose of R-oxybutynin will be 2.5 mg in this study.

A detailed description of the chemistry, pharmacology, efficacy, and safety of AD109 is provided in the Investigator's Brochure.

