9.5 Appendix 5: List of Abbreviations

AHI apnea-hypopnea index

AE adverse event

Bang Body mass index, Age, Neck circumference, and Gender criteria

BMI body mass index

CFR Code of Federal Regulations
CNS central nervous system

CPAP continuous positive air pressure

CYP2D6 cytochrome P450 2D6 CYP3A4 cytochrome P450 3A4

DSM-5 Diagnostic and Statistical Manual of Mental Disorders, 5th edition

ECG electrocardiogram
EEG electroencephalogram

eCRF electronic case report form(s)

EDC electronic data capture

EOS end of study

FSH follicle-stimulating hormone GCP Good Clinical Practice

HB Hypoxic burden

HRT hormone replacement therapy

ICF informed consent form

ICH International Conference on Harmonisation

IEC Independent Ethics CommitteeIND Investigational New DrugIRB Institutional Review Board

IRT Interactive Response Technology

OSA obstructive sleep apnea

OTC over-the-counter

MAOI monoamine oxidase inhibitor
NREM non-rapid eye movement
PK pharmacokinetic(s)
PSG polysomnography

QHS 1 dose every night at bedtime

REM rapid eye movement
SAE serious adverse event
SAP Statistical Analysis Plan
SoA Schedule of Activities

STOP Snoring, Tiredness, Observed apnea, and Blood pressure criteria

SUSAR suspected unexpected serious adverse reaction

ULN upper limit of normal

US United States

WOCBP woman of childbearing potential

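### The overdose definition in Protocol 7.4 is ambiguous and, read literally, leaves two 37.5/2.5 tablets on one night (75/5 mg) outside it

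*Protocol*

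**What the plan says.** Protocol 7.4 sets the only overdose threshold in either document: a dose of atomoxetine "greater than 75 mg and of R-oxybutynin chloride greater than 2.5 mg more frequently than QHS will be considered an overdose". Protocol Appendix 5 expands the abbreviation: "QHS 1 dose every night at bedtime".

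When an event meets the definition, 7.4 requires immediate contact with the Medical Monitor and close monitoring until drug is no longer detectable. It also requires a plasma sample if the Medical Monitor asks for one, and an eCRF entry for the size and duration of the excess.

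Dosing in this trial is not nightly. Protocol 6.1 says "One tablet of co-formulated atomoxetine and R-oxybutynin or matching placebo is taken" before bedtime, and the Schedule of Activities places study treatment at Visits 3, 4 and 5 only, with the footnote "Each washout period is a minimum of 7 days". The active tablets are 37.5 mg / 2.5 mg and 75 mg / 2.5 mg.

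Protocol Appendix 3 says when an overdose is reportable as an adverse event, but gives no dose threshold. The SAP has no overdose definition.

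**The concern.** Two features of the sentence cause trouble. The limits are joined by *and*, so on a literal reading both must be exceeded. The frequency phrase refers to a nightly regimen that nobody in this trial follows, and it is unclear whether it qualifies the second limit, both limits, or neither.

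Both active tablets carry the same 2.5 mg of R-oxybutynin, while the lower one carries half the atomoxetine limit. Doubling the lower tablet therefore doubles R-oxybutynin without taking atomoxetine past its limit.

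At stake is whether the steps in 7.4 start. Under Appendix 3, an accidental overdose without symptoms is not itself an adverse event, so 7.4 is the specific route for capturing it. The doubled drug is the anticholinergic one, and Protocol 7.2 states: "Adverse events of special interest include effects on urine outflow".

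**Working it through.** There is no planned figure to reproduce. The check adds up the dose and tests it against each way of reading the sentence.

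**Inputs.** Tablet strengths 37.5/2.5 and 75/2.5 mg (Protocol 6.1); limits of 75 mg atomoxetine and 2.5 mg R-oxybutynin (Protocol 7.4).

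**Dose from two lower-strength tablets.**
- Atomoxetine: 37.5 + 37.5 = 75 mg; 75/75 = 1.0, so *above 75* is false.
- R-oxybutynin: 2.5 + 2.5 = 5 mg; 5/2.5 = 2.0, so *above 2.5* is true.
- Joined by *and*: false and true = false, not an overdose.
- Joined by *or*: false or true = true, an overdose.

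**Is 75/5 mg an overdose?** Two tablets swallowed together at bedtime are taken here as not more frequent than nightly; two taken at separate times in the night are taken as more frequent.

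| Reading of 7.4 | Taken together | Taken separately |
|---|---|---|
| 1. Both limits needed, frequency phrase ignored | No | No |
| 2. Both limits needed, frequency phrase applies to both | No | No |
| 3. Atomoxetine limit alone, or R-oxybutynin limit with the frequency phrase | No | Yes |
| 4. Either limit, frequency phrase applies to both | No | Yes |
| 5. Either limit, frequency phrase a separate criterion or dropped | Yes | Yes |

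Two tablets taken together are caught only under reading 5. That reading treats the limits as a list and also detaches the frequency phrase from the R-oxybutynin limit.

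**The reworded rule** (more than one tablet on a dosing night, or either limit exceeded). A single tablet of either strength gives at most 75/2.5 mg and is not an overdose. Three tablet types make six two-tablet combinations:
- Two active tablets: 75/5, 112.5/5 and 150/5 mg. All are caught, by tablet count and by the R-oxybutynin limit.
- At least one placebo: 0/0, 37.5/2.5 and 75/2.5 mg. All are caught by tablet count alone, although neither limit is exceeded. These three are the unnecessary calls.

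**The case against.** **The list reading.** The word *of* is repeated before each drug, which reads naturally as two separate limits. The second follow-up step in 7.4 also refers to either or both drugs being detectable, so the section itself treats the components separately. The intent is easy to infer, and a sensible investigator may well call anyway. This stands as a reason to call the text ambiguous instead of saying that it plainly excludes 75/5 mg. It does not clear the wording, because the frequency phrase must also be set aside before the case is caught.

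**Blinding.** The investigator and the staff who give the drug are blinded (SAP 3.2.2). Faced with two tablets, they could rarely know that both were the lower strength, so they would seldom be in a position to decide that 7.4 does not apply. This stands and lowers the risk. It also shows that a milligram rule alone is hard for them to use.

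**Other safeguards.** Protocol 6.2 says "only authorized site staff may supply or administer study treatments", and requires accountability and reconciliation, which should reveal an extra tablet. Participants are on overnight PSG after dosing and are telephoned during washout (Protocol 4.1). Misuse is a stopping criterion (6.6.1), and signs or sequelae of a suspected overdose are reportable (Appendix 3). The SAP lists protocol deviations (5.2) and exposure (7.1) by participant. All of this stands. What could be lost is the immediate call, the monitoring and the dedicated eCRF entry for a symptom-free error.

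**Conclusion.** Wrong as written, minor. The definition is ambiguous and mismatched to a single-dose crossover. Its literal reading leaves out one specific error, 75/5 mg, in which R-oxybutynin is 2.0 times its limit and atomoxetine 1.0 times. Because the sentence triggers safety actions, correcting it is more than clerical. The practical risk is low, and endpoints, sample size and analysis are unaffected. The conclusion assumes a reader who takes *and* literally, or who ties the frequency phrase to the R-oxybutynin limit.

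A reader might infer three stronger points that the documents do not support:

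- *That the rule lets a participant dose every night.* An overdose definition does not authorize dosing. The Schedule of Activities does that, and an off-schedule tablet is a protocol deviation whatever 7.4 says.
- *That 75/5 mg is shown to be harmful.* Protocol 4.2 says "the R-enantiomer of oxybutynin confers about 2-fold the anticholinergic activity of the racemate", so 5 mg would correspond to about 5 × 2 = 10 mg of racemate, and Protocol 2.1 cites "doses of racemic oxybutynin between 1.5 and 5 mg" in earlier studies. But the ratio concerns anticholinergic activity only, the 5 mg is the top of the range studied and not a safety ceiling, and no harm data at 75/5 mg are given.
- *That larger tablet errors are missed too.* A 75/2.5 tablet with any other active tablet (112.5/5 or 150/5 mg) exceeds both limits. It escapes only if the frequency phrase is made to govern both, which the text does not clearly say. Those errors are not part of this point.

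**What to change.** Replace the definition in 7.4 with: *An overdose is more than one study tablet on any dosing night, or more than 75 mg of atomoxetine, or more than 2.5 mg of R-oxybutynin.* Delete the frequency phrase. Leave a single tablet given early or off schedule as a protocol deviation; a correct tablet given inside the 7-day washout should not start overdose procedures.

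The tablet count lets blinded staff apply the rule at once, so no added unblinding step is needed. The milligram limits serve cases where the dose is already known.

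The cost is one reworded sentence in one protocol section. Nothing changes for participants dosed as scheduled. The downside is an occasional Medical Monitor call that proves unnecessary because a tablet was placebo, as in three of the six two-tablet combinations.
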